Amylase and/or lipase elevation, Grade 2	Amylase and/or lipase > 1.5–2.0 × ULN: • Continue RO7121661.
	Monitor amylase and lipase weekly.
	• For prolonged elevation (e.g., > 3 weeks), consider treatment with 10 mg/day oral prednisone or equivalent.
	Asymptomatic with amylase and/or lipase $> 2.0-5.0 \times ULN$:
	Treat as a Grade 3 event.
Amylase and/or lipase	Withhold RO7121661 for up to 12 weeks after event onset. ^a
elevation, Grade 3 or 4	Refer patient to GI specialist.
	Monitor amylase and lipase every other day.
	 If no improvement, consider treatment with 1–2 mg/kg/day oral prednisone or equivalent.
	If event resolves to Grade 1 or better, resume RO7121661.b
	 If event does not resolve to Grade 1 or better while withholding RO7121661, permanently discontinue RO7121661 and contact Medical Monitor.
	For recurrent events, permanently discontinue RO7121661 and contact Medical Monitor.

GI = gastrointestinal.

- a RO7121661 may be withheld for a longer period of time (i.e., > 12 weeks after event onset) to allow for corticosteroids (if initiated) to be reduced to ≤ 10 mg/day oral prednisone or equivalent. The Investigator determines an acceptable length of the extended period of time. The Medical Monitor is available to the Investigator to advise and answer questions in this regard.
- b If corticosteroids have been initiated, they must be tapered over ≥1 month to ≤10 mg/day oral prednisone or equivalent before RO7121661 can be resumed.

Table 7 Management Guidelines for Pancreatic Events, Including Pancreatitis (cont.)

Event	Management
Immune-mediated pancreatitis, Grade 2 or 3	 Withhold RO7121661 for up to 12 weeks after event onset. ^a Refer patient to GI specialist. Initiate treatment with 1–2 mg/kg/day IV methylprednisolone or equivalent and convert to 1–2 mg/kg/day oral prednisone
	or equivalent upon improvement. • If event resolves to Grade 1 or better, resume RO7121661. b
	If event does not resolve to Grade 1 or better while withholding RO7121661, permanently discontinue RO7121661 and contact Medical Monitor.
	For recurrent events, permanently discontinue RO7121661 and contact Medical Monitor.
Immune-mediated pancreatitis, Grade 4	 Permanently discontinue RO7121661 and contact Medical Monitor. Refer patient to GI specialist.
	 Initiate treatment with 1–2 mg/kg/day IV methylprednisolone or equivalent and convert to 1–2 mg/kg/day oral prednisone or equivalent upon improvement.
	If event does not improve within 48 hours after initiating corticosteroids, consider adding an immunosuppressive agent.
	If event resolves to Grade 1 or better, taper corticosteroids over ≥1 month.

GI = gastrointestinal.

- a RO7121661 may be withheld for a longer period of time (i.e., > 12 weeks after event onset) to allow for corticosteroids (if initiated) to be reduced to ≤ 10 mg/day oral prednisone or equivalent. The Investigator determines an acceptable length of the extended period of time. The Medical Monitor is available to the Investigator to advise and answer questions in this regard.
- b If corticosteroids have been initiated, they must be tapered over ≥1 month to ≤10 mg/day oral prednisone or equivalent before RO7121661 can be resumed.

DERMATOLOGIC EVENTS

Treatment-emergent rash may be associated with RO7121661. A dermatologist should evaluate persistent and/or severe rash or pruritus. A biopsy should be considered unless contraindicated. Management guidelines for dermatologic events are provided in Table 8.

 Table 8
 Management Guidelines for Dermatologic Events

Event	Management	
Dermatologic event, Grade 1	 Continue RO7121661. Consider treatment with topical corticosteroids and/or other symptomatic therapy (e.g., antihistamines). 	
Dermatologic event, Grade 2	 Continue RO7121661. Consider patient referral to dermatologist. Initiate treatment with topical corticosteroids. Consider treatment with higher-potency topical corticosteroids if event does not improve. 	
Dermatologic event, Grade 3	 Withhold RO7121661 for up to 12 weeks after event onset. ^a Refer patient to dermatologist. Initiate treatment with 10 mg/day oral prednisone or equivalent, increasing dose to 1–2 mg/kg/day if event does not improve within 48–72 hours. If event resolves to Grade 1 or better, resume RO7121661. ^b If event does not resolve to Grade 1 or better while withholding RO7121661, permanently discontinue RO7121661 and contact Medical Monitor. 	
Dermatologic event, Grade 4	Permanently discontinue RO7121661 and contact Medical Monitor.	

a RO7121661 may be withheld for a longer period of time (i.e., > 12 weeks after event onset) to allow for corticosteroids (if initiated) to be reduced to ≤ 10 mg/day oral prednisone or equivalent. The Investigator determines an acceptable length of the extended period of time. The Medical Monitor is available to the Investigator to advise and answer questions in this regard.

NEUROLOGIC DISORDERS

Myasthenia gravis and Guillain-Barré syndrome may be observed with RO7121661. Patients may present with signs and symptoms of sensory and/or motor neuropathy. Diagnostic work-up is essential for an accurate characterization to differentiate between alternative etiologies. Management guidelines for neurologic disorders are provided in Table 9.

b If corticosteroids have been initiated, they must be tapered over ≥1 month to ≤10 mg/day oral prednisone or equivalent before RO7121661 can be resumed.

Table 9 Management Guidelines for Neurologic Disorders

Event	Management	
Immune- mediated neuropathy, Grade 1	Continue RO7121661.Investigate etiology.	
Immune- mediated neuropathy, Grade 2	 Withhold RO7121661 for up to 12 weeks after event onset. a Investigate etiology. Initiate treatment as per institutional guidelines. If event resolves to Grade 1 or better, resume RO7121661. b If event does not resolve to Grade 1 or better while withholding RO7121661, permanently discontinue RO7121661 and contact Medical Monitor. 	
Immune- mediated neuropathy, Grade 3 or 4	 Permanently discontinue RO7121661 and contact Medical Monitor. Initiate treatment as per institutional guidelines. 	
Myasthenia gravis and Guillain-Barré syndrome (any grade)	 Permanently discontinue RO7121661 and contact Medical Monitor. Refer patient to neurologist. Initiate treatment as per institutional guidelines. Consider initiation of 1–2 mg/kg/day oral or IV prednisone or equivalent. 	

a RO7121661 may be withheld for a longer period of time (i.e., > 12 weeks after event onset) to allow for corticosteroids (if initiated) to be reduced to ≤10 mg/day oral prednisone or equivalent. The Investigator determines an acceptable length of the extended period of time. The Medical Monitor is available to the Investigator to advise and answer questions in this regard.

IMMUNE-MEDIATED MENINGOENCEPHALITIS

Immune-mediated meningoencephalitis may be associated with the administration of RO7121661. Immune-mediated meningoencephalitis should be suspected in any patient presenting with signs or symptoms suggestive of meningitis or encephalitis, including, but not limited to, headache, neck pain, confusion, seizure, motor or sensory dysfunction, and altered or depressed level of consciousness. Encephalopathy from metabolic or electrolyte imbalances needs to be distinguished from potential meningoencephalitis resulting from infection (bacterial, viral, or fungal) or progression of malignancy, or secondary to a paraneoplastic process.

b If corticosteroids have been initiated, they must be tapered over ≥1 month to ≤10 mg/day oral prednisone or equivalent before RO7121661 can be resumed.

All patients being considered for meningoencephalitis should be urgently evaluated with a CT scan and/or MRI scan of the brain to evaluate for metastasis, inflammation, or edema. If deemed safe by the treating physician, a lumbar puncture should be performed and a neurologist should be consulted.

Patients with signs and symptoms of meningoencephalitis, in the absence of an identified alternate etiology, should be treated according to the guidelines in Table 10.

Table 10 Management Guidelines for Immune-Mediated Meningoencephalitis

Event	Management	
Immune-mediated meningoencephalitis, all grades	 Permanently discontinue RO7121661 and contact Medical Monitor. Refer patient to neurologist. 	
	 Initiate treatment with 1–2 mg/kg/day IV methylprednisolone or equivalent and convert to 1–2 mg/kg/day oral prednisone or equivalent upon improvement. 	
	If event does not improve within 48 hours after initiating corticosteroids, consider adding an immunosuppressive agent.	
	If event resolves to Grade 1 or better, taper corticosteroids over ≥1 month.	

RENAL EVENTS

Immune-mediated nephritis may be associated with the administration of RO7121661. Eligible patients must have adequate renal function, and renal function, including serum creatinine, should be monitored throughout study treatment. Patients with abnormal renal function should be evaluated and treated for other more common etiologies (including prerenal and postrenal causes, and concomitant medications such as non-steroidal anti-inflammatory drugs). Refer the patient to a renal specialist if clinically indicated. A renal biopsy may be required to enable a definitive diagnosis and appropriate treatment.

Patients with signs and symptoms of nephritis, in the absence of an identified alternate etiology, should be treated according to the guidelines in Table 11.

Table 11 Management Guidelines for Renal Events

Event	Management	
Renal event, Grade 1	 Continue RO7121661. Monitor kidney function, including creatinine, closely until values resolve to within normal limits or to baseline values. 	

Renal event, Grade 2	 Withhold RO7121661 for up to 12 weeks after event onset. ^a Refer patient to renal specialist.
	 Initiate treatment with corticosteroids equivalent to 1–2 mg/kg/day oral prednisone.
	If event resolves to Grade 1 or better, resume RO7121661.
	If event does not resolve to Grade 1 or better while withholding RO7121661, permanently discontinue RO7121661 and contact Medical Monitor.
Renal event, Grade 3 or 4	Permanently discontinue RO7121661 and contact Medical Monitor.
	Refer patient to renal specialist and consider renal biopsy.
	 Initiate treatment with corticosteroids equivalent to 1–2 mg/kg/day oral prednisone.
	If event does not improve within 48 hours after initiating corticosteroids, consider adding an immunosuppressive agent.
	• If event resolves to Grade 1 or better, taper corticosteroids over ≥ 1 month.

- a RO7121661 may be withheld for a longer period of time (i.e., > 12 weeks after event onset) to allow for corticosteroids (if initiated) to be reduced to the equivalent of ≤ 10 mg/day oral prednisone. The Investigator determines an acceptable length of the extended period of time. The Medical Monitor is available to the Investigator to advise and answer questions in this regard.
- ^b If corticosteroids have been initiated, they must be tapered over ≥ 1 month to the equivalent of ≤ 10 mg/day oral prednisone before RO7121661 can be resumed.

IMMUNE-MEDIATED MYOSITIS

Immune-mediated myositis may be associated with the administration of RO7121661. Myositis or inflammatory myopathies are a group of disorders sharing the common feature of inflammatory muscle injury; dermatomyositis and polymyositis are among the most common disorders. Initial diagnosis is based on clinical (muscle weakness, muscle pain, skin rash in dermatomyositis), biochemical (serum creatine kinase increase), and imaging (electromyography/MRI) features, and is confirmed with a muscle biopsy.

Patients with signs and symptoms of myositis, in the absence of an identified alternate etiology, should be treated according to the guidelines in Table 12.

Table 12 Management Guidelines for Immune-Mediated Myositis

Event	Management	
Immune- mediated myositis, Grade 1	 Continue RO7121661. Refer patient to rheumatologist or neurologist. Initiate treatment as per institutional guidelines. 	
Immune- mediated myositis, Grade 2	 Withhold RO7121661 for up to 12 weeks after event onset a and contact Medical Monitor. Refer patient to rheumatologist or neurologist. Initiate treatment as per institutional guidelines. Consider treatment with corticosteroids equivalent to 1–2 mg/kg/day IV methylprednisolone and convert to 1–2 mg/kg/day oral prednisone or equivalent upon improvement. If corticosteroids are initiated and event does not improve within 48 hours after initiating corticosteroids, consider adding an immunosuppressive agent. If event resolves to Grade 1 or better, resume RO7121661. b If event does not resolve to Grade 1 or better while withholding RO7121661, permanently discontinue RO7121661 and contact Medical Monitor. 	

a RO7121661 may be withheld for a longer period of time (i.e., > 12 weeks after event onset) to allow for corticosteroids (if initiated) to be reduced to the equivalent of ≤ 10 mg/day oral prednisone. The Investigator determines an acceptable length of the extended period of time. The Medical Monitor is available to the Investigator to advise and answer questions in this regard.

If corticosteroids have been initiated, they must be tapered over ≥ 1 month to the equivalent of ≤ 10 mg/day oral prednisone before RO7121661 can be resumed.

Table 12 Management Guidelines for Immune-Mediated Myositis (cont.)

Immunemediated myositis, Grade 3

- Withhold RO7121661 for up to 12 weeks after event onset a and contact Medical Monitor.
- Refer patient to rheumatologist or neurologist.
- Initiate treatment as per institutional guidelines. Respiratory support may be required in more severe cases.
- Initiate treatment with corticosteroids equivalent to 1–2 mg/kg/day IV methylprednisolone, or higher-dose bolus if patient is severely compromised (e.g., cardiac or respiratory symptoms, dysphagia, or weakness that severely limits mobility); convert to 1–2 mg/kg/day oral prednisone or equivalent upon improvement.
- If event does not improve within 48 hours after initiating corticosteroids, consider adding an immunosuppressive agent.
- If event resolves to Grade 1 or better, resume RO7121661.
- If event does not resolve to Grade 1 or better while withholding RO7121661, permanently discontinue RO7121661 and contact Medical Monitor.
- For recurrent events, treat as a Grade 4 event.

Immunemediated myositis, Grade 4

- Permanently discontinue RO7121661 and contact Medical Monitor.
- Refer patient to rheumatologist or neurologist.
- Initiate treatment as per institutional guidelines. Respiratory support may be required in more severe cases.
- Initiate treatment with corticosteroids equivalent to 1–2 mg/kg/day IV methylprednisolone, or higher-dose bolus if patient is severely compromised (e.g., cardiac or respiratory symptoms, dysphagia, or weakness that severely limits mobility); convert to 1–2 mg/kg/day oral prednisone or equivalent upon improvement.
- If event does not improve within 48 hours after initiating corticosteroids, consider adding an immunosuppressive agent.
- If event resolves to Grade 1 or better, taper corticosteroids over ≥ 1 month.
- a RO7121661 may be withheld for a longer period of time (i.e., > 12 weeks after event onset) to allow for corticosteroids (if initiated) to be reduced to the equivalent of ≤ 10 mg/day oral prednisone. The Investigator determines an acceptable length of the extended period of time. The Medical Monitor is available to the Investigator to advise and answer questions in this regard.
- b If corticosteroids have been initiated, they must be tapered over ≥ 1 month to the equivalent of ≤ 10 mg/day oral prednisone before RO7121661 can be resumed.

HEMOPHAGOCYTIC LYMPHOHISTIOCYTOSIS AND MACROPHAGE ACTIVATION SYNDROME

Immune-mediated reactions may involve any organ system and may lead to hemophagocytic lymphohistiocytosis (HLH) and macrophage activation syndrome (MAS).

Participants with suspected HLH should be diagnosed according to published criteria by McClain and Eckstein (2014). A participant should be classified as having HLH if five of the following eight criteria are met:

- Fever ≥ 38.5°C
- Splenomegaly
- Peripheral blood cytopenia consisting of at least two of the following:
 - Hemoglobin < 90 g/L (9 g/dL)
 - Platelet count $< 100 \times 109/L (100 000/\mu L)$
 - $ANC < 1.0 \times 10^{9}/L (1000/\mu L)$
- Fasting triglycerides > 2.992 mmol/L (265 mg/dL) and/or fibrinogen < 1.5 g/L (150 mg/dL)
- Hemophagocytosis in bone marrow, spleen, lymph node, or liver
- Low or absent natural killer cell activity
- Ferritin > 500 mg/L (500 ng/mL)
- Soluble interleukin 2 (IL-2) receptor (soluble CD25) elevated ≥ 2 standard deviations above age-adjusted laboratory-specific norms

Participants with suspected MAS should be diagnosed according to published criteria for systemic juvenile idiopathic arthritis by Ravelli et al. 2016. A febrile participant should be classified as having MAS if the following criteria are met:

- Ferritin > 684 mg/L (684 ng/mL)
- At least two of the following:
 - Platelet count $\leq 181 \times 10^9/L (181,000/\mu L)$
 - AST ≥ 48 U/L
 - Triglycerides > 1.761 mmol/L (156 mg/dL)
 - Fibrinogen $\leq 3.6 \text{ g/L} (360 \text{ mg/dL})$

Participants with suspected HLH or MAS should be treated according to the guidelines in Table 13.

Table 13 Management Guidelines for Suspected Hemophagocytic Lymphohistiocytosis or Macrophage Activation Syndrome

Event	Management	
Suspected HLH or MAS	Permanently discontinue study drug and contact Medical Monitor.	
	Consider participant referral to hematologist.	
	• Initiate supportive care, including intensive care monitoring if indicated per institutional guidelines.	
	• Consider initiation of IV corticosteroids, an immunosuppressive agent, and/or anti-cytokine therapy.	
	• If event does not respond to treatment within 24 hours, contact Medical Monitor and initiate treatment as appropriate according to published guidelines (La Rosée 2015; Schram and Berliner 2015; La Rosée et al. 2019).	
	 If event resolves to Grade 1 or better, taper corticosteroids over ≥ 1 month. 	

 $HLH = Hemophagocytic \ lymphohistiocytosis; \ IV = Intravenous; \ MAS = Macrophage \ activation \ syndrome.$

REFERENCES

- La Rosée P. Treatment of hemophagocytic lymphohistiocytosis in adults. Hematology Am Soc Hematol Educ Protram. 2015:190-6.

 https://www.uptodate.com/contents/clinical-features-and-diagnosis-of-hemophagocytic-lymphohistiocytosis.

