Appendix 4 Clinical Laboratory Tests

The tests detailed in Table 1 will be performed by the local laboratory unless otherwise specified.

Protocol-specific requirements for inclusion or exclusion of participants are detailed in Sections 5.1 and 5.2, respectively, of the protocol.

Additional tests may be performed at any time during the study as determined necessary by the Investigator or required by local regulations.

All study-required safety laboratory assessments will be performed by local laboratories, with the exception of the following:

• Analysis of IgE and tryptase samples will be performed centrally and locally.

 Table 1
 Protocol-Required Safety Laboratory Assessments

Laboratory Assessments	Parameters
Hematology	Leucocytes, erythrocytes, hemoglobin, hematocrit, platelets, differential count (neutrophils, eosinophils, basophils, monocytes, lymphocytes, other cells).
Clinical Chemistry	Sodium, potassium, chloride, bicarbonate, glucose, urea or BUN, creatinine, protein, albumin, phosphate, calcium, total and direct bilirubin, alkaline phosphatase, ALT, AST, urate, LDH, CRCL (determined by Cockcroft Gault formula) ^a , GGT, Magnesium, CRP, ferritin.
Coagulation	Including PT (optional), INR, and aPTT; additional coagulation parameters (i.e., anti thrombin III [antigenic or chromogenic], fibrinogen, PT, fibrin degradation products, D dimer) maybe be assessed according to clinical judgment.
Viral Serology	HIV (specific tests HIV-1 antibody, HIV-1/2 antibody, HIV-2 antibody), hepatitis B surface antigen (HBsAg), total hepatitis B core antibody (HBcAb), hepatitis C virus (HCV) antibody.
Lipids	Cholesterol, LDL cholesterol, HDL cholesterol, triglycerides.
Thyroid Hormones	Free T4, free T3, TSH
Infusion related reactions	IgE and tryptase and cytokine samples will be collected for central and local analysis if a participant experiences a Grade≥2 IRR for the first time with the second or subsequent study drug infusion or with clinical signs of hypersensitivity reaction at any time of the conduct of the study. A second sample for central IgE/tryptase analysis will be collected approximately 48 hours after onset of the reaction.
Quantitative Immunoglobulins	lgA, lgG, lgM, lgE
Urinalysis	Specific gravity Dipstick: pH, glucose, protein, blood, ketones, bilirubin, urobilinogen, nitrite, leukocyte esterase

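### The HLH and MAS ferritin criteria in Appendix 6 each print two values that differ 1000-fold, so classification depends on which unit is read

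*Combined protocol and SAP*

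**What the plan says.** The HLH and MAS section of Appendix 6 is listed in the summary of changes as an addition in this amendment, so it is current text.

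- **HLH rule:** "A participant should be classified as having HLH if five of the following eight criteria are met". One of the eight is "Ferritin > 500 mg/L (500 ng/mL".
- **MAS rule:** "A febrile participant should be classified as having MAS if the following criteria are met". The criteria are "Ferritin > 684 mg/L (684 ng/mL" and at least two of four further laboratory findings (platelets, AST, triglycerides, fibrinogen).
- **Management:** "Participants with suspected HLH or MAS should be treated according to the guidelines in Table 13". The single row of that table is for suspected HLH or MAS, and its first instruction is "Permanently discontinue study drug and contact Medical Monitor".
- **Laboratory:** Appendix 4, Table 1 includes ferritin in the clinical chemistry panel ("Magnesium, CRP, ferritin") and gives no unit. Safety laboratory tests are run locally, apart from IgE and tryptase, which are also analysed centrally.

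**The concern.** Each ferritin line presents its two figures as the same threshold in different units, and they are not the same. The appendix directs that suspected cases be diagnosed by these lists, so the figures are operative.

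A site that applies the leading mg/L value and a site that applies the bracketed ng/mL value could classify the same participant differently. Under Appendix 3, Section 1.2, a known diagnosis is entered as the adverse event in place of its separate signs and symptoms. An inconsistent HLH or MAS classification therefore carries into the adverse event data. Those data are a primary endpoint in dose escalation and a secondary endpoint in Part B (Section 3, Table 4).

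**Working it through.** **Inputs.** All come from the HLH and MAS section of Appendix 6: the two ferritin lines, the five-of-eight HLH rule, the MAS rule, the lead-in to Table 13, and the other unit pairs in the same lists.

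**1. Can the printed equality be reproduced?** No.

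1 mg = 1,000,000 ng and 1 L = 1,000 mL, so 1 mg/L = 1,000,000 / 1,000 = 1,000 ng/mL.

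| Criterion | First value, converted | Bracketed value | Ratio |
|---|---|---|---|
| HLH | 500 mg/L × 1,000 = 500,000 ng/mL | 500 ng/mL (= 0.5 mg/L) | 1000 |
| MAS | 684 mg/L × 1,000 = 684,000 ng/mL | 684 ng/mL (= 0.684 mg/L) | 1000 |

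**2. Is this a general problem with the lists?** No. The other pairs were converted as a control.

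- Hemoglobin: 90 g/L / 10 = 9 g/dL, as printed.
- Fibrinogen, HLH ("fibrinogen < 1.5 g/L (150 mg/dL"): 1.5 × 100 = 150 mg/dL, as printed.
- Fibrinogen, MAS: 3.6 × 100 = 360 mg/dL, as printed.
- Triglycerides: 265 / 2.992 = 88.57 and 156 / 1.761 = 88.59 mg/dL per mmol/L, so the two lines imply the same conversion factor.
- Neutrophils: 1.0 × 10⁹/L = 1,000 per µL, as printed.
- Platelets, MAS: 181 × 10⁹/L = 181,000 per µL, as printed.
- Platelets, HLH: the exponent is missing in the text as read (109 where 10⁹ is evidently meant). With 10⁹, 100 × 10⁹/L = 100,000 per µL, as printed.

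Only the two ferritin pairs fail.

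**3. Consequence for MAS.** The rule is fever AND ferritin AND at least two of four others. Ferritin cannot be replaced by another criterion. A febrile participant with ferritin above 684 and up to 684,000 ng/mL who meets the other criteria is MAS on the bracketed reading and not MAS on the mg/L reading.

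**4. Consequence for HLH.** Ferritin is one of eight criteria and is not mandatory.

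- Combinations with at least five of eight: C(8,5) + C(8,6) + C(8,7) + C(8,8) = 56 + 28 + 8 + 1 = 93.
- Combinations with at least five of the other seven: C(7,5) + C(7,6) + C(7,7) = 21 + 7 + 1 = 29.
- Combinations that qualify only because ferritin is counted (ferritin plus exactly four of seven): C(7,4) = 35.

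For a participant whose ferritin lies above 500 and up to 500,000 ng/mL, those 35 patterns are HLH on one reading and not on the other. These are counts of patterns, not probabilities.

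**5. Consequence for Table 13.** Both the lead-in sentence and the row label refer to suspected HLH or MAS. Permanent discontinuation is tied to suspicion, not to meeting the ferritin-based lists, so the unit conflict does not change its stated trigger.

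**The case against.** **Text extraction.** The strongest objection is that mg/L may be a misread µg/L. One changed character would make both pairs exact, because 1 µg/L = 1 ng/mL. The micro signs that survive in these two lists all sit in formula-formatted spans, whereas the ferritin lines are plain text. Amendment text is set in an italic face, which could invite such a misreading, and an exponent has visibly been lost in the HLH platelet line. This cannot be excluded from the text alone. Against it, the same mismatch appears on two separate lines, and plain-text micro signs survive elsewhere, for example in Sections 4.4 and 5.1. The contradiction stands on the text available, and the PDF will settle the question.

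**Discontinuation.** A reader might infer that on the mg/L reading the permanent-discontinuation rule would not trigger. The documents do not support this, because Table 13 applies on suspicion.

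**MAS never diagnosable.** A reader might also infer that MAS could never be diagnosed on the mg/L reading. That needs a maximum attainable ferritin, which the documents do not give. They support only that the requirement would be 1000 times the bracketed value.

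**Practical harm.** The ng/mL value is printed on the same line, the criteria are attributed to published sources, and no site reporting unit is documented. Actual divergence between sites is therefore a possibility and has not been shown. The DLT definition in Section 4.1.3 does not use these criteria. This limits the weight of the point without removing the contradiction.

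**Conclusion.** Wrong as written, subject to the PDF check. Both ferritin criteria state two thresholds exactly 1000-fold apart, and this follows from unit conversion with no further assumption.

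On the mg/L reading, MAS classification would require ferritin above 684,000 ng/mL. The HLH route is narrowed but not closed, since five of the other seven criteria still suffice.

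The effect is confined to HLH and MAS diagnosis, classification and the adverse event recording that follows. That recording effect rests on the assumption that some sites would apply the mg/L figure, because the documents do not say which unit laboratories report. The management instruction in Table 13 and the efficacy analyses are not affected. The point deserves correction because these are newly added operative criteria for a serious toxicity, and it is more than a matter of typography.

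**What to change.** First compare both ferritin lines with the sponsor's PDF. If a micro sign was lost in reading, nothing in the plan needs to change. If mg/L is what is printed, reconcile the two lines so that each gives a single threshold in equivalent units, verified against the publications the appendix cites for HLH and MAS. Which value is intended is for the sponsor to establish, and none is proposed here.

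The cost is two corrected lines in Appendix 6. No change to design, sample size or analysis is needed.
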